5.3.2 Subject Groups

After applying the inclusion and exclusion criteria, our analysis will focus on the following cohorts.

Index Event 1a

- U-500R Syringe Initiators Cohort: Patients who initiated U-500R syringe administration (index event 1a) on their index date.

Index Event 1b

- U-500R Kwikpen Initiators Cohort: Patients who initiated U-500R Kwikpen administration (index event 1b) on their index date.

Index Event 2

- U-500R Device Switchers Cohort: Patients who switched from U-500R syringe to Kwikpen will be included in this cohort.

Note: U-500R syringe/ Kwikpen initiators cohorts who were identified based on the index event 1a or 1b were U-500R naïve patients who did not have any evidence of U-500R use prior to the index date; whereas patients in U-500R device switchers cohort identified from index event 2 had been exposed to U-500R prior to the index date due to U-500R syringe use.

5.4 Time Periods

The study period will range from 01APR2013-31MAR2018 for VHA and LCED; and 01JUL2013-30JUN2018 for Truven MarketScan claims. The identification period will be 01JAN2014-30JUN2017 for VHA and LCED; and 01APR2014-30SEP2017 for Truven MarketScan claims; the baseline and follow-up periods will be 9 months pre- and 9 months post-index date, respectively (Figures 1-3).

[2018-7241 Study Identifier] Observational Study Protocol**5.5 Variables/Measures**

Table 3 presents the study variables and operational definitions.

Table 3 Variables and Definitions

Variable	Source	Definition
Exposure		
Insulin use	Truven: Outpatient pharmacy claims table VHA: Pharmacy file	Index Event 1a : any insulin use other than U-500R in the pre-index and U-500R syringe use in the post-index period; Index Event 1b : any insulin use other than U-500R in the pre-index and U-500R Kwikpen use in the post-index period; and Index Event 2 : U-500R syringe use in the pre-index and U-500R Kwikpen use in the post-index period.
Baseline Characteristics*		
Age	Truven: Inpatient service table, outpatient service table, outpatient pharmacy claims table VHA: Enrollment file	Age will be retained in the dataset as a continuous variable for groups aged 18-25, 26-35, 36-45, 46-55, 56-64, and ≥ 65 years.
Sex	Truven: Inpatient service table, outpatient service table, outpatient pharmacy claims table VHA: Enrollment file	A flag will be created for male and female patients.
Race (only VHA)	VHA: Enrollment file	A flag will be created for White, Black, and other race patients.
U.S Region (only Truven)	Truven: Inpatient service table, outpatient service table, outpatient pharmacy claims table	A flag will be created for patients belonging to Northeast, Northcentral, South and West regions
Medicare eligibility (Only Truven)	From Truven	A flag will be created for patients who are enrolled in Truven Medicare
Body mass index (BMI)	VHA: Vital Status file	BMI on the index date will be calculated and reported as a continuous variable.
Quan-Charlson comorbidity index (CCI) Score ¹⁶	Truven: Inpatient service table, outpatient service table VHA: Inpatient and outpatient files	Quan-CCI score will be constructed using enhanced ICD-9/10-CM codes for 17 different comorbid conditions.

[2018-7241 Study Identifier] Observational Study Protocol

Individual Comorbidities ¹⁷	Truven: Inpatient service table, outpatient service table VHA: Inpatient and outpatient files	A flag will be created using ICD-9/10-CM codes (Appendix 1) for patients diagnosed in the baseline period with any of the following individual comorbidities: retinopathy, nephropathy, neuropathy, coronary artery disease, peripheral vascular disease, congestive heart failure, hypertension, depression, obesity, or malignant tumor.
Health Economics Outcomes Research (HEOR) Outcomes		
Observed TDD in claims	Truven: Outpatient pharmacy claims table VHA: Pharmacy file	
The observed insulin TDD will be calculated as the total number of insulin units/total unique days of supply as recorded in claims and will be calculated both in the pre-and post-index periods among the U-500R syringe initiators, U-500R Kwikpen initiators, and the U-500R device switchers. TDD will be reported both as continuous and categorical variable.
 
For U-500R syringe initiators (index event 1a): Total insulin units correspond to all the insulin units in pre-index and post-index periods respectively Additionally the TDD of U-500R syringe only will be reported in the post-index period
 
For U-500R Kwikpen initiators (index event 1b): Total insulin units correspond to all the insulin units in pre-index and post-index periods respectively Additionally the TDD of U-500R Kwikpen only will be reported in the post-index period
 
For U-500R device switchers (index event 2): For device switchers the total insulin units correspond only to the total units of U-500R syringe use in the pre-index period and U-500R Kwikpen in the post-index period
 
Note:

[2018-7241 Study Identifier] Observational Study Protocol

		For the unique days supply in patients with evidence of a basal-bolus regimen, or basal/bolus-pre-mixed or basal/bolus-U-500R the overlap days will be adjusted for the concomitant use of basal and bolus insulins, but will not be adjusted within basal and within bolus insulins.
Observed average daily dose (ADD) in claims	Truven: Outpatient pharmacy claims table VHA: Pharmacy file	
The observed insulin ADD will be calculated both in the pre-and post-index periods among the U-500R syringe initiators, U-500 Kwikpen initiators, and the U-500R device switchers. ADD will be reported both as continuous and categorical variable.
 
Pre-index ADD: total number of insulin units/ the total number of days in the pre-index period.
 
Post-index ADD: total number of insulin units/ the total number of days in the post-index period.
 
Additionally the ADD of U-500R syringe only and the U-500R Kwikpen only will be reported in the U-500R syringe initiators and Kwikpen initiators respectively.
 
Note: Total insulin units calculation in based on the similar approach as described in TDD.

Adherence	Truven: Outpatient pharmacy claims table VHA: Pharmacy file	
Adherence to insulin will be assessed using the proportion of days covered (PDC), and reported in categories of 0-20%, 20-40%, 40-60%, 60-80%, and 80%-100%. PDC will be calculated both in the pre-and post-index periods among the U-500R syringe initiators, U-500 Kwikpen initiators ,and the U-500R device switchers.
 
For U-500R syringe initiators (index event 1a):

[2018-7241 Study Identifier] Observational Study Protocol

		
PDC before U-500R initiation will be calculated as the number of days covered by the prescription claims of insulin (any insulin)/total days in the pre-index period;
 
PDC after U-500R initiation will be calculated as the number of days covered by the prescription claims of insulin (any insulin)/total days in the post-index period.
 
For U-500R Kwikpen initiators (index event 1b):
 
PDC before U-500R initiation will be calculated as the number of days covered by the prescription claims of insulin (any insulin)/total days in the pre-index period;
 
PDC after U-500R initiation will be calculated as the number of days covered by the prescription claims of insulin (any insulin)/total days in the post-index period.
 
For U-500R device switchers (index event 2):
 
PDC before switching will be defined as the number of days covered by the prescription claims of insulin (U-500R syringe)/total days in the pre-index period;
 
PDC after switching will be defined as the number of days covered by the prescription claims of insulin (U-500R Kwikpen)/total days in the post index period
 
Note: For the calculation of PDC in patients with evidence of a basal-bolus regimen, basal/bolus-premixed, or basal/bolus-U-500R, the overlap days will be adjusted for the concomitant use of basal and bolus insulins, but will not be adjusted within basal and within bolus insulins.

--	--	---

[2018-7241 Study Identifier] Observational Study Protocol

Persistence/time to discontinuation	Truven: Outpatient pharmacy claims table VHA: Pharmacy file	Persistence will be defined as the percentage of patients continuing on the index medication in the post-index period. Patient is considered to discontinue if there is no refill of the index medication within 60 days from the run-out date (date of last prescription + days of supply) i.e, a gap of >60 days from the run out date. The run-out date will be the discontinuation date. Time to discontinuation will be defined as the total number of days from the index date to the discontinuation date during the post-index period.
Abandonment/fill rates	Truven: Outpatient pharmacy claims table VHA: Pharmacy file	The average number of insulin prescription fills will be calculated in the pre- and post-index periods among all the study cohorts.
Claim gaps	Truven: Outpatient pharmacy claims table VHA: Pharmacy file	The average gap between prescription fills of insulins will be calculated in the pre- and post-index periods among all the study cohorts.
Concomitant medications ^{18,19,20}	Truven: Outpatient pharmacy claims table VHA: Pharmacy file	A flag will be created for patients prescribed antihyperglycemic agents (AHA): thiazolidinediones, sulfonylureas, biguanides, meglitinides, alpha-glucosidase inhibitors, DPP-4 inhibitors, bile acid sequestrants, fixed-dose combinations, GLP-1 receptor agonists, and amylin agonists (Appendix 1).

[2018-7241 Study Identifier] Observational Study Protocol

HbA1c ²¹	VHA: Lab file	The HbA1c value in the baseline and follow-up period for each index event will be reported. Baseline HbA1c (pre-index HbA1c) will be the HbA1c measurement -90/+30 days of the index date. For patients with multiple HbA1c measurements within this period, the measurement taken closest to the index event date will be reported as the baseline HbA1c value. The follow-up HbA1c value will be the HbA1c measurement taken furthest in the time period after the 30 day-post index event date. However, based on the sample size, HbA1c within 2 months prior to the end of the study follow-up will be considered as the post-index HbA1c.
Hypoglycemic events	Truven: Inpatient service table, outpatient service table VHA: Inpatient and outpatient files, Lab file and Pharmacy file	Hypoglycemia events in the pre-index and post-index period will be evaluated using the ICD-9 codes from the Ginde algorithm (Appendix 1) ²² or the presence of a cutoff of blood glucose ≤ 70 mg/dL, or any evidence of intramuscular glucagon administration (Appendix 1). Hypoglycemia event occurred on or after the index date will be considered as the follow-up hypoglycemia event; and hypoglycemia event occurred on or prior to - 1 day of the index date will be considered as the baseline hypoglycemia event. Number of hypoglycaemia events per patient per year (PPPY) will be reported in both the pre-index and post-index periods.
Prescribed TDD	Linked Truven claims and EMR data:	The prescribed physician TDD will be calculated, and will be reported both as continuous and categorical variable.

[2018-7241 Study Identifier] Observational Study Protocol

All-cause health care total and out-of-pocket costs	Truven: Inpatient service table, outpatient service table, outpatient pharmacy claims table	All-cause health care costs for total and out-of-pocket costs including inpatient costs, outpatient costs, pharmacy costs, total costs (inpatient + outpatient + pharmacy), out-of-pocket inpatient costs, out-of-pocket outpatient costs, out-of-pocket pharmacy costs and total out-of-pocket costs (inpatient + outpatient + pharmacy) will be computed among T2DM patients before and after U-500R syringe initiation and U-500R Kwikpen initiation. Costs will be adjusted to 2018 US dollars using the annual medical care and drug costs components of the Consumer Price Index (CPI) to reflect inflation.
---	---	--

Note: When comparing the TDD, ADD, adherence, fill rates and claim gaps in the pre vs post-index periods among the U-500R device switchers, only the claims corresponding to U-500R (syringe in the pre-index and Kwikpen in the post-index) will be considered. To be more specific we will be looking only at the treatment patterns of U-500R alone rather than the regimen.

However, for the U-500R initiators, the regimen use (use of different types of insulin) in the pre-index period will be compared to the regimen use (U-500R + other insulins) in the post-index period.

[2018-7241 Study Identifier] Observational Study Protocol**6. Sample Size and Statistical Methods****6.1 Determination of Sample Size**

The preliminary sample sizes for the VHA databases from 2013-2018 are shown below. This study will use the most recently available 5 years of data.

Table 4. Preliminary Sample Size

Database	Counts
VHA (01APRIL2013-31MARCH2018)	
T2DM (ICD-9: 250.x0, 250.x2) + Humulin R U-500 Kwikpen (NDC: 00002882427, 00002882459)	4,120
≥2 HbA1c measurements	4,066
T2DM + Humulin R U-500 Vial (NDC: 00002850101)	5,863
≥2 HbA1c measurements	5,718

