- Exclude patients who had claims indicating TDD above 2000 units/day at any time in the pre-index or post-index periods.

Sample Selection Criteria for U-500R Device Switchers from Syringe to Kwikpen [Index Event 2]

- Include patients who had ≥ 1 claim for U-500R Kwikpen administration in the identification period (VHA and LCED: 01JAN2014-30JUN2017; Truven: 01APR2014-30SEP2017)–the first prescription claim for U-500R Kwikpen administration will be designated as the Index Event 2, and the date will be designated as the index date;
- Include patients who had ≥ 2 claim with an ICD-9/10-CM code (Appendix 1) for T2DM in any position (primary/secondary) at any time prior to the index date;
- Exclude patients who had both T1DM and T2DM, had no OADs (Appendix 1) other than metformin, and the ratio between the number of T1DM and T2DM claims > 0.5 at any time in the study period (VHA and LCED: 01APR2013-31MAR2018; Truven: 01JUL2013-30JUN2018);
- Include patients who were aged ≥ 18 years on the index date;
- Include patients who had continuous health plan enrollment with medical and pharmacy benefits for ≥ 9 months pre- and post-index event;
- Include patients who had ≥ 1 prescription claim for U-500R vial use in the 9-month baseline period;

[2018-7241 Study Identifier] Observational Study Protocol

- Include patients who had ≥ 1 HbA1c measurement within 90-day pre-index event or 30-day post-index event; and
- Include patients who had ≥ 1 HbA1c measurement after the 30-day post-index period;
 - Patients with ≥ 1 HbA1c measurement after the 30-day post-index and within 30 days prior to the end of the 9-months follow-up period will be flagged; and
 - Patients with ≥ 1 HbA1c measurement after the 30-day post-index and within 2 months prior to the end of the 9-months follow-up period will be flagged;
- Exclude patients who had ≥ 1 claim for U-500R Kwikpen administration in the 9-month baseline period;
- Exclude patients who had ≥ 1 claim with a ICD-9/10-CM code (Appendix 1) for secondary diabetes, gestational diabetes, diabetes complicating pregnancy, childbirth, or puerperium, or non-clinical diabetes at any time during the 9-month baseline period;
- Exclude patients who had claims indicating pump use (Appendix 2) in the identification period;
- Exclude patients who had claims indicating TDD exceeding 2000 units/day at any time in the pre-index or post-index periods.

Note:

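### In device switchers, pre-index PDC and ADD divide vial-only use by a full 9 months, so time before the vial was started counts as non-adherence

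*Protocol*

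**What the plan says.** Section 5.4 sets the windows: "the baseline and follow-up periods will be 9 months pre- and 9 months post-index date, respectively". Table 3 (Section 5.5) then defines, for device switchers, pre-index PDC as the "number of days covered by the prescription claims of insulin (U-500R syringe)/total days in the pre-index period" and post-index PDC as the "number of days covered by the prescription claims of insulin (U-500R Kwikpen)/total days in the post index period". ADD is the "total number of insulin units/ the total number of days in the pre-index period" before index and the "total number of insulin units/ the total number of days in the post-index period" after it. For switchers, Table 3 and its closing note restrict the counted claims to the vial before and the Kwikpen after. The Objective 1 model note in Section 6.4.1 confirms that PDC runs over the whole of each period.

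Eligibility is looser than the denominator. For switchers, Section 5.3.1 asks only to "Include patients who had ≥ 1 prescription claim for U-500R vial use in the 9-month baseline period", and "the first prescription claim for U-500R Kwikpen administration will be designated as the Index Event 2", so day 0 of follow-up is itself a fill of the counted product.

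For initiators the pre-index numerator takes any insulin: "number of days covered by the prescription claims of insulin (any insulin)/total days in the pre-index period". The protocol does not say whether supply dispensed before the window opens is credited, or whether a last fill running past the end of a window is cut off.

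**The concern.** The two windows have equal length but are not alike. The post-index window always opens on a fill of the counted product. The pre-index window opens on a calendar date tied to no fill, and for a switcher it may open months before the vial was first dispensed. Days when that patient was on another insulin, perhaps perfectly adherent, then count against vial adherence.

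Adherence before versus after is named in Primary Objective 1. It is tested by paired t-test and is the outcome of the Objective 1 mixed model. Primary Objective 2 asks whether adherence played a role in HbA1c change, with switchers included, and Step 2 of that mediation analysis takes a significant association between time and adherence as support for mediation. A bias in the definition can supply that association with no change in behaviour. In switchers it would be read as a benefit of the device.

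**Working it through.** The protocol gives no expected PDC or ADD, so there is no figure to reproduce. Its dates give windows of 273 to 275 days (for example 01APR2013 to 01JAN2014 = 275; 30JUN2017 to 31MAR2018 = 274). I use 274.

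**1. Ceiling for a switcher.** With m months on the vial and no day missed, pre-index PDC is at most m/9:

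| Months on vial | Pre-index ceiling | Post-index ceiling |
|---|---|---|
| 1 | 11% | 100% |
| 2 | 22% | 100% |
| 3 | 33% | 100% |
| 6 | 67% | 100% |

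In days, 60/274 = 22%. This needs no assumption about fill length or carry-in.

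**2. Cohort mean.** If a share f starts the vial at uniform times within the window and everyone is fully adherent, the mean loss is f × 1/2: 5 points at f = 10%, 12.5 at 25%, 25 at 50%.

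**3. Incomplete coverage.** Simulation with identical refill behaviour before and after, so the true change is zero. Assumed: 30-day fills, 80% coverage, carried-in supply credited.

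| Share starting in window | PDC change (points) | ADD ratio, post/pre |
|---|---|---|
| 0% | +1.6 | 1.07 |
| 10% | +5.1 | 1.11 |
| 25% | +11.2 | 1.20 |
| 50% | +20.6 | 1.36 |

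At a 25% share, scenarios with other fill lengths and coverage give about +12 to +17 points.

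**4. Initiators and other established users.** With carry-in credited, the PDC change is 0 at full coverage. At 80% to 60% coverage it depends on how the index date relates to the refill cycle. If unrelated, it is about 2 to 3 points (30-day fills) or 4 to 9 (90-day). If the index fill is simply the next refill, it is about 2 to 5 or 7 to 11 points. Without carry-in it is generally larger: at 80% coverage with an unrelated index date, +5.7 points (30-day) or +17.8 (90-day).

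**5. ADD and fill counts, all cohorts.** Under full adherence with 30-day fills, follow-up holds fills on days 0, 30, ..., 270, which is 10, against 274/30 = 9.13 expected before: ratio 10/9.13 = 1.09. With 90-day fills it is 4 against 274/90 = 3.04: ratio 1.31. The excess is the last fill, counted whole.

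**6. Would the bias reach significance?** Pairs for 80% power at two-sided 0.05: n = (SD × 2.80/d)². For d = 10 points and an assumed SD of 25, about 50. For d = 3 and an assumed SD of 20, about 350.

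**7. Opposing force.** With 25% of patients stopping at a uniform time after index (30-day fills, 80% coverage), the net PDC change is -7.2, +2.2 and +11.3 points at 0%, 25% and 50% starting in the window.

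**The case against.** A reader might infer that adherence and dose must rise significantly in every cohort. The documents do not support that, for these reasons:

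- **Carry-in.** The protocol nowhere says that supply from before the window goes uncredited. That may be settled in the SAP. The larger PDC figures for established users depend on it. The VHA and LCED data do start exactly 9 months before identification opens, but that matters only for the earliest index dates. Section 5.1 calls the Kwikpen recently available, so earlier data should mostly exist for its users.
- **Initiators.** They are credited for any insulin in both periods, so the switcher argument does not carry over in full.
- **Dose.** TDD, not ADD, is the dose measure in Primary Objective 1 and in the models. It divides by days of supply and does not share this denominator.
- **Claim gaps.** These are intervals between fills with no window denominator. No effect on them is shown.
- **Costs.** Primary Objective 3 does not include switchers, so their bias cannot enter the cost mediation.
- **Direction of the observed result.** Discontinuation counts as uncovered time. Vial use continuing after the switch is ignored. Both lower post-index PDC.

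All of these stand and limit the point. None removes the switcher problem, which follows from the eligibility rule and the denominator as written. Opposing forces of unknown size also do not cancel a bias; they make the net change uninterpretable.

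**Conclusion.** The point holds for device switchers. Their pre-index PDC and ADD mix adherence with time since starting the vial, and the comparison with follow-up is biased upward. The individual ceilings (11% to 67% for 1 to 6 months on the vial) follow from the definitions alone. The cohort effect depends on the share starting within the window, which is not given: about f/2 at full adherence, and roughly 11 to 17 points at an assumed 25%. That is enough to supply the time-adherence association in Step 2 of the HbA1c mediation without any change in behaviour.

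In initiators the PDC bias is secondary: nil at full coverage with carry-in credited, otherwise about 2 to 5 points (30-day fills) or up to 11 (90-day) at 80% to 60% coverage, and larger if carry-in is not credited. ADD and fill counts are inflated in all cohorts by counting whole fills from a window that opens on a fill. Fill lengths, coverage, SDs and start shares are all assumptions. This is a bias in the definition, not a prediction that the observed change will be positive.

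**What to change.** In Table 3:

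- **Switchers:** start the pre-index PDC and ADD denominator at the first vial fill in the baseline and end it on day -1.
- **Initiators:** do the same from the first insulin fill, or credit carried-in supply where the data exist, and state which.
- **All cohorts:** count only supply days, and prorated units, that fall inside each window.
- **Sensitivity analysis for switchers:** restrict to patients with a stated minimum time on the vial, and count vial plus pen after the switch. Keep the device-specific result alongside it.

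In zero-change simulations, starting at the first qualifying fill brings the PDC artefact to about 0 to 3 points in most scenarios. It can overcorrect, by up to 6 points with 90-day fills at 60% coverage. ADD also needs the prorating; with both changes, pre and post ADD agree at full refilling.

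The cost is wording and programming, with no new data. The downside is a shorter, variable pre-index denominator that is imprecise for patients with little time on the vial. The minimum-time restriction loses some of them, which is why it belongs in a sensitivity analysis.

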5.3. Study Population

5.3.1 Selection Criteria

Patient selection criteria for the U-500R Syringe Initiators [Index Event 1a]:

- Include patients who had ≥ 1 prescription claim for U-500R vial during the identification period (VHA and LCED: 01JAN2014-30JUN2017; Truven: 01APR2014-30SEP2017)—the first prescription claim for U-500R vial will be designated as index Event 1a (U-500R syringe initiation), and the date will be designated as the index date;
- Include patients who had ≥ 2 claims with an ICD-9/10-CM code (Appendix 1) for T2DM in any position (primary/secondary) at any time prior to the index date;
- Exclude patients who had both T1DM and T2DM, had no oral anti-diabetic drug (OADs; Appendix 1) other than metformin, and the ratio between the number of T1DM and T2DM claims > 0.5 at any time in the study period (VHA and LCED: 01APR2013-31MAR2018; Truven: 01JUL2013-30JUN2018);
- Include patients who were aged ≥ 18 years on the index date;
- Include patients who had continuous health plan enrollment with medical and pharmacy benefits for ≥ 9 months pre- and post-index event;
- Exclude patients with no evidence of insulin including U-500R (any type; Table 2) in the 9 months pre-index period (baseline);

[2018-7241 Study Identifier] Observational Study Protocol

- Exclude patients with ≥ 1 prescription claim for U-500R use in the 9 months pre-index period;
- Include patients who had ≥ 1 prescription claim for any insulin other than U-500R in the 9-month pre-index period;
- Include patients who had ≥ 1 HbA1c measurement within 90-day pre-index or 30-day post-index event;
- Include patients who had ≥ 1 HbA1c measurement after the 30-day post-index period at any time in the 9-months follow-up period;
 - Patients with ≥ 1 HbA1c measurement after the 30-day post-index and within 30 days prior to the end of the 9-months follow-up period will be flagged; and
 - Patients with ≥ 1 HbA1c measurement after the 30-day post-index and within 2 months prior to the end of the 9-months follow-up period will be flagged;
- Exclude patients who had ≥ 1 claim with a ICD-9/10-CM code (Appendix 1) for secondary diabetes, gestational diabetes, diabetes complicating pregnancy, childbirth, or puerperium, or non-clinical diabetes at any time during the 9-month baseline period;
- Exclude patients who had claims indicating pump use (Appendix 2) in the 9-month post-index (follow-up) period;

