Zero-inflated negative binomial mixed model will be used to evaluate factors associated with number of hypoglycemia events PPPY in the pre- and post-index periods among U-500R syringe initiators, U-500R Kwikpen initiators, and U-500R device switchers. Zero-inflated negative binomial distribution is a mixture of a binary distribution that is degenerate at zero and an ordinary count distribution such as negative binomial. In cases of outcome variable being repeatedly measured from the individual subjects, zero inflated models are extended to include random effects to account for the correlation among the repeated measures within a subject. In the current model, the number of hypoglycemia events which might have more zeroes (for example not every patient might have a lab visit for glucose) and is measured at two time intervals (before and after the index event; U-500R initiation/device switch), will be considered the dependent variable. Observed TDD, and HbA1c will be considered as the time varying covariates in the model (measured both in the before and after index date), and the time-independent covariates will include the demographic and clinical characteristics.

The complete list of covariates will include:

- age
- sex
- race
- BMI
- baseline CCI score

[2018-7241 Study Identifier] Observational Study Protocol

- observed TDD from claims
- HbA1c
- time (pre/post)

Note: Age, sex, race, BMI, and CCI score will be assessed during pre-index period. Observed TDD and HbA1c will be calculated during the entire pre-index and post-index periods, respectively. Pre-index HbA1c will be defined as the HbA1c measurement -90/+30 days of the index date. For patients with multiple HbA1c measurements within this period, the measurement taken closest to the index event date will be reported as the pre-index HbA1c value. Post-index HbA1c will be defined as the HbA1c within 2 months of the end of the follow-up period.

Research Objective 2: Secondary Objective 2bDescriptive Analysis

Treatment outcomes (HbA1c and number of hypoglycemic events) and prescriber behavior (observed TDD in claims and prescribed TDD from the physician) will be analyzed descriptively and quarterly before and after U-500R syringe initiation and U-500R Kwikpen initiation, and before and after U-500R device switch from syringe to Kwikpen.

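### Hypoglycemia follow-up starts on the date of the prescription claim, so a low glucose recorded that day before the first dose counts as post-index (minor)

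*Protocol*

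**What the plan says.** Section 5.5, Table 3 divides hypoglycemia at the index date. On the follow-up side: "Hypoglycemia event occurred on or after the index date will be considered as the follow-up hypoglycemia event". On the baseline side: "hypoglycemia event occurred on or prior to - 1 day of the index date will be considered as the baseline hypoglycemia event". Every day therefore belongs to exactly one period, and the index date belongs to follow-up. An event may be a diagnosis code, "the presence of a cutoff of blood glucose ≤ 70 mg/dL", or glucagon administration.

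The index date is a claim date. Section 5.3.1 says for the syringe cohort that "the first prescription claim for U-500R vial will be designated as index Event 1a", and the Kwikpen and device-switch cohorts are indexed in the same way on the first Kwikpen claim. Section 5.4 sets the windows: "the baseline and follow-up periods will be 9 months pre- and 9 months post-index date, respectively". The data limitations in Section 5.2 acknowledge that a filled claim does not show that the drug was taken.

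Secondary Objective 2a compares events per patient per year before and after the index date within each cohort. Hypoglycemia is also the only adverse event to be collected (Section 7.1). The protocol has no rule for the order of events within the index date and no analysis that leaves that date out.

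**The concern.** An event that precedes the first dose from the index fill belongs to the previous regimen: other insulin in the initiators, U-500R by syringe in the switchers. On the index date, the rule in Table 3 assigns it to the new one.

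This matters more than one ordinary day would if contacts and tests fall on that date. A glucose at or below the cutoff is enough to make an event, so the count depends partly on who is tested; Section 6.4.1 itself notes that not every patient may have a glucose laboratory visit. The comparison is before-after within the patient, and no day in the pre-index period is tied to a treatment change in the same way. Any excess of pre-dose events on the index date therefore enters the post-index count with nothing to offset it, and a larger sample does not remove it.

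**Working it through.** The protocol states no hypoglycemia rate, no share of patients tested on the index date and no target difference. There is thus no planned figure to reproduce, and the calculation below is a sensitivity analysis on assumed inputs.

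**Calendar check.** Nine months before 01JAN2014 is 01APR2013, and nine months after 30JUN2017 is 30MAR2018, within the stated end of 31MAR2018 (VHA and LCED). Nine months before 01APR2014 is 01JUL2013, and nine months after 30SEP2017 is 30JUN2018 (Truven). The dates fit follow-up from the index date. A start on day +1 still ends by 30JUN2018 in the tightest case, because 30JUN2018 is day +273 for an index date of 30SEP2017.

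**Inputs**
- Period length: 274 days including the index date, so T = 274/365.25 = 0.750 year.
- λ, true rate, the same before and after: 0.25 to 2 events per patient-year (assumed).
- f, share of patients with a pre-dose low on the index date beyond an ordinary day's events: 0.1% to 2% (assumed).
- n: 4,066, the VHA Kwikpen count with at least two HbA1c values in Table 4. This is an upper bound, before the other criteria. A value of 1,000 is shown as a smaller illustration.
- k, negative binomial dispersion: 1 to 3 (assumed).

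**Effect on the ratio when the true ratio is 1.** With m = λT, the rule as written gives (m + f)/m. At λ = 0.25, m = 0.1875, and f = 0.02 gives 0.2075/0.1875 = 1.107. At λ = 2, m = 1.500, and f = 0.001 gives 1.501/1.500 = 1.001.

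| λ per patient-year | f = 0.1% | f = 0.5% | f = 1% | f = 2% |
|---|---|---|---|---|
| 0.25 | 1.005 | 1.027 | 1.053 | 1.107 |
| 0.5 | 1.003 | 1.013 | 1.027 | 1.053 |
| 1 | 1.001 | 1.007 | 1.013 | 1.027 |
| 2 | 1.001 | 1.003 | 1.007 | 1.013 |

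**On the rate scale** the shift is f/T: 0.001/0.750 = 0.0013 to 0.02/0.750 = 0.0267 events per patient-year.

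**Against sampling error.** The standard error of the mean paired difference is √(2(m + km²)/n), with the periods taken as independent. At λ = 0.25, k = 1 and n = 4,066 it is √(2 × 0.2227/4,066) = 0.0105, so f = 0.02 is a shift of 1.9 standard errors. Over all the assumed inputs the shift is 0.02 to 1.9 standard errors at n = 4,066 and 0.01 to 0.95 at n = 1,000. Positive correlation within patients would shrink the standard error and make the shift larger in these units.

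**The two ways to handle the index date.** Moving it to baseline gives m/(m + f), which is 0.904 to 0.999 when the truth is 1. Leaving it out of both windows gives 1.000.

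**The case against.** Starting follow-up at the index date is a common convention, and the rule is neither an error in the text nor a contradiction. It agrees with the rest of the plan, where time to discontinuation also runs from the index date, and counting from that date is the cautious choice for a safety outcome. A sensitivity analysis may also sit in a statistical analysis plan that is not shown. All of this stands, and it is why the point is only minor.

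The mechanism is conditional. If the prescribing visit came before the fill, its low glucose is already baseline. The protocol does not say how often visit and fill coincide. A reader might infer that prescribing visits and their tests cluster on the fill date; nothing in the document shows that. The required HbA1c near the index date shows laboratory contact around it, not on it.

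The size can also be overstated by counting every index-date event as extra. An ordinary day carries λ/365.25 events per patient, or 0.0007 at λ = 0.25 and 0.0055 at λ = 2. If f is read as all pre-dose lows, not as the excess, the top ratio falls to 1 + (0.0200 − 0.0007)/0.1875 = 1.103, and at λ = 2 with f = 0.1% no excess remains.

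A reader might also see a conflict with the HbA1c row, where "Baseline HbA1c (pre-index HbA1c) will be the HbA1c measurement -90/+30 days of the index date" and "the measurement taken closest to the index event date will be reported as the baseline HbA1c value", so that one blood draw could supply a pre-index HbA1c and a post-index event. The documents do not support that reading. The HbA1c window runs to day +30 and so is no ruling on the order of events within the index date. If the two rows had to match, hypoglycemia through day +30 would be baseline as well. The HbA1c window does not cause the misclassification.

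**Conclusion.** The point holds in a limited form and is minor. Table 3 scores as post-index any event on the claim date, including one that precedes the first dose. Where contact and fill share a date, the error from such events runs one way. In the initiators it counts against U-500R. In the device switchers, who use U-500R in both periods, it counts against the Kwikpen only.

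Under the assumed inputs the post/pre ratio is inflated by about 0.1% to 11%. It stays below 3% if the rate is at least 1 per patient-year and no more than 2% of patients have a pre-dose low that day. The upper end needs both a low event rate and a high share of index-date lows. The protocol supports neither end of the range, and a claim of material bias would go beyond it.

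**What to change.** In Section 5.5, Table 3, start hypoglycemia follow-up on day +1, keep baseline ending on day −1, and leave the index date out of both windows. Adjust the person-time in the per-patient-per-year rate to match, in the descriptive comparison and in the Secondary Objective 2a count model. Report the number of index-date events by cohort. If the sponsor prefers to keep the present rule for the main analysis, specify this version as a sensitivity analysis.

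The index date should not be moved to baseline. That would credit a true first-day event after the new product to the previous regimen, and would turn the inflation into a deficit of similar size.

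The cost is small: 1 of 274 follow-up days, about 0.4%, and no data beyond the study period. True same-day events after the first dose leave the main rate but stay visible in the index-date count.
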